9.1.2 Demographics

The following demographic information collected for the Core Study will be used for the current study: date of birth, sex and race (as allowed per local regulations).

9.1.3 Medical History

Medical history collected for the Core Study will be used for the current study. New information about relevant, significant medical history discovered during/after the Core Study will be collected and is defined as any condition or disease that:

- May affect the condition under study.
- Is ongoing on entry into the study.

9.1.4 Inpatient Epilepsy-Related Hospitalizations

The number of inpatient hospitalizations that are, in the Investigator's opinion, due to epilepsy will be recorded in the patient's CRF and through the Serious Adverse Event (SAE) reporting process.

9.1.5 Concomitant Medication

Details of all current medication, including AEDs, recorded at the end of the Core Study ('End of Treatment', 'End of Taper Period' or Follow-up visit, as applicable) and medications, including AEDs, taken during the last 2 weeks of the inter-study period ("prior medications") will also be recorded for the current study and at each subsequent study visits. Any changes in concomitant medication during the study must be recorded in the CRF at study visits. Patients should stop taking any prohibited therapy prior to enrollment, as defined in [Section 8.3](#).

If seizure freedom is achieved with use of GWP42003-P during the study, the Investigator can consider reducing the dose of concomitant AEDs after consultation with the GW medical monitor.

9.1.6 Physical Examination

Physical examinations will include height and body weight measurements.

9.1.7 Vital Signs

Vital sign measurements, taken in a sitting position at rest for 5 minutes, will be completed alongside the physical examination. Blood pressure must be recorded using the same arm throughout the study.

9.1.8 12-Lead Electrocardiogram

An ECG will be performed, after 5 minutes in a supine position. A physician must review the ECG and any abnormal findings considered to indicate significant medical history or AEs must be recorded appropriately in the CRF. Additional ECG measurements can be taken at any time during the study, if clinically indicated.

9.1.9 Clinical Laboratory Sampling

Laboratory tests will include hematology, biochemistry and urinalysis (provided urine can be obtained). Analysis of all clinical blood samples and pregnancy tests (using serum at the 'End of Treatment'/Withdrawal visit) will be conducted at a central clinical laboratory. However, in order to confirm normal hepatic function before OLE dosing commences, an additional blood sample may be taken to analyze ALT, AST, TBL and INR at a local laboratory.

Urine samples for biochemistry will be analyzed at the study center by use of a dipstick with any relevant findings being sent for further urinalysis at the central laboratory (urinalysis, microscopy, culture and sensitivity, as applicable). Urine pregnancy tests (using a dipstick) will be performed at the study center at Visit 1. In cases where urine samples cannot be analyzed at site due to local regulations, a full set of urine samples should be sent to the central laboratory for analysis.

The Investigator and study monitor will be provided with a list of the normal ranges used by the testing laboratory for all variables assayed during the study and a statement of accreditation (or similar) for the laboratory. Clinical laboratory sample parameters are detailed in [Table 9.1.9-1](#).

Throughout the study additional blood samples may be collected for measurement of plasma concentrations of concomitant AEDs. The decision on whether or not to assess plasma concentrations of concomitant AEDs will be left to the Investigator's clinical judgment. Analysis may be done at local or central laboratories and data

collected in the CRF. Central laboratory analysis results will not be released to the Investigator.

Table 9.1.9-1 Hematology, Biochemistry and Urinalysis			
Biochemistry (serum)	Hematology (whole blood)	Urinalysis (urine)	Pregnancy Test
Alanine aminotransferase (ALT)	Hematocrit	Bilirubin	(Serum or Urine)
Albumin	Hemoglobin	Blood	
Alkaline phosphatase	Mean cell volume	Glucose	
Aspartate aminotransferase (AST)	Mean corpuscular hemoglobin	Ketones	
Calcium	Platelets	Nitrites	
Creatinine	Red blood cell count	pH	
Estimates of glomerular filtration rate	White blood cell count with automated differential	Protein	
Gamma glutamyl transferase		Specific gravity	
Glucose		Urobilinogen	
HDL-cholesterol			
Insulin-like growth factor-1 (IGF-1)			
Potassium			
Prolactin			
Prothrombin time (plasma)			
Sodium			
Total bilirubin (TBL)			
Total protein			
Triglycerides			
Urea (blood urea nitrogen [BUN])			

Investigators at study centers will be notified of safety laboratory test results. All laboratory results will be reviewed and the reports signed by an Investigator. Any results considered to be of clinical significance must be addressed and followed up as clinically appropriate. See [Section 12.8](#) for guidance on evaluation of potential drug-induced liver injury. All laboratory results considered to represent an AE must be documented on the CRF.

Repeat samples will be taken, if required, for clinical follow-up or if the sample is lost or damaged. Any abnormal end of treatment clinical laboratory result of clinical significance must be repeated at regular intervals until it returns to normal, or until an Investigator is satisfied that the abnormality is not related to the IMP and needs no further investigation.

Sample volume requirements and processing procedures will be detailed in a separate laboratory manual. The patient/caregiver must be advised that it may not be safe for the patient to undertake further blood tests within one month of any study-related blood draws and to inform the Investigator if they suffered any blood loss during the one-month period leading up to a planned blood draw.

9.1.10 Interactive Voice Response System

The IVRS will be used to collect patient reported diary data (refer to [Section 9.1.12](#)) and to manage IMP supply. A member of the study team must contact the IVRS at each clinic visit in order to obtain dispensing information and to provide completion/taper/premature termination information.

9.1.11 Questionnaires and Assessments Completed at Scheduled Visits

Questionnaires should be completed by the patient or the caregiver, as appropriate. The same person should complete/answer the questionnaires/assessments in order to maintain consistency. The C-SSRS will be administered by a trained rater.

9.1.11.1 Vineland Adaptive Behavior Scales (Second Edition)

The Vineland-II is an individually administered instrument for assessing adaptive behaviors. Communication, Daily Living Skills, Socialization, and Motor Skills will be assessed by the caregiver using a rating scale. Vineland-II assessments will be performed for all patients irrespective of whether or not they completed the Vineland-II during their Core Study.

9.1.11.2 Quality of Life in Childhood Epilepsy (18 Years of Age and Younger) or Quality Life in Epilepsy (19 Years of Age and Older)

The QOLCE and the QOLIE are composed of 16 and 31 subscales, respectively, assessing 7 domains of Health Related Quality of Life (physical function, social function, emotional well-being, cognition, behavior, general health and general quality of life). The QOLCE (and QOLIE, if completed by the caregiver) must be completed by a person who interacts with the patient on a consistent, daily basis. Quality of life assessments will be performed for all patients irrespective of whether or not they completed during their Core Study. The questionnaires should take 20–30 minutes to complete.

9.1.11.3 Subject/Caregiver Global Impression of Change

The S/CGIC, as appropriate, will be performed for all patients irrespective of whether or not it was completed during their Core Study. The patient or patient's caregiver will use the description of their/the patient's overall condition made during the Core Study (prior to commencement of IMP). If the memory aid is not available from the Core Study then the patient/caregiver will be asked to write a brief description from memory, if possible, at Visit 1 as an aid for subsequent visits. It is preferred that the same person performs this assessment at each visit.

The CGIC comprises the following question to be rated on a 7-point scale:

- Since your child started treatment, please assess the status of your child's overall condition (comparing their condition now to their condition before treatment) using the scale below.

The SGIC comprises the following question to be rated on a 7-point scale:

- Since you started treatment, please assess the status of your overall condition (comparing your condition now to your condition before treatment) using the scale below.

The markers are: Very Much Improved; Much Improved; Slightly Improved; No Change; Slightly Worse; Much Worse; Very Much Worse.

If the main caregiver is not available at the appropriate visit then this information can be captured over the telephone ideally on the day of the visit or otherwise within 3 days.

9.1.11.4 Subject/Caregiver Global Impression of Change in Seizure Duration

The S/CGICSD comprises a question to be rated on a 3-point scale for each seizure subtype:

CGICSD:

- Since the patient started treatment, please assess the average duration of the patient's seizures (comparing their condition now to their condition before treatment at the Baseline of the Core Study) using the scale below.

SGICSD:

- Since you started treatment, please assess the average duration of your seizures (comparing their condition now to their condition before treatment at the Baseline of the Core Study) using the scale below.

The markers are: Average duration of seizures has decreased; Average duration of seizures has stayed the same; Average duration of seizures has increased.

The patient/caregiver would have been asked to assess and note the average duration of the patient's seizures at the Baseline of the Core Study as a memory aid for subsequent visits. If the memory aid is not available from the Baseline of the Core Study then the patient/caregiver should do this from memory, if possible, and complete a memory aid at Visit 1.

If the main caregiver is not available at the appropriate visit then this information can be captured over the telephone, ideally on the day of the visit or otherwise within 3 days.

9.1.11.5 Columbia-Suicide Severity Rating Scale (Six Years of Age and Older)

The definitions of behavioral suicidal events used in this scale are based on those used in the Columbia-Suicide History Form. Questions are asked on suicidal behavior, suicidal ideation and intensity of ideation. Questioning will be in relation to the last assessment (Since Last Visit).

The C-SSRS is to be completed by the Investigator or his/her qualified designee at every visit as indicated in the Schedule of Assessments (see [APPENDIX 1](#)); "qualified designee" is defined as anyone who has completed the C-SSRS training within the past 2 years. The survey should be completed by the same assessor, where possible, throughout the study. The Children's C-SSRS will be used for patients aged 6–18 (inclusive) while the C-SSRS will be used for patients aged 19 and older. For patients that become 6 years old during this OLE trial, the Children's Baseline C-SSRS (employing questions in relation to lifetime experience) should be completed at the next trial visit. Questioning at all subsequent visits will be in relation to the last assessment (Children's Since Last Visit).

9.1.11.6 Cognitive Assessment Battery

The items that comprise the cognitive assessment battery are age specific. The age of the patient at entry will be the age used when choosing the items to be administered. Children and adults are to complete the battery as able. It is expected that a number of patients will only be able to complete part of the battery and some may not be able to complete any of it. Parents and/or caregivers are to complete certain items. The cognitive assessment battery items will only be administered at a sub-group of centers that have the expertise to conduct the assessments (ideally before any other study procedures but can be completed on a separate day, if necessary, within 3 days of the visit). Each assessment will need to be conducted by an experienced

psychometrician. A summary of the battery is as shown below in [Table 9.1.11.6-1](#) and [Table 9.1.11.6-2](#). Items will only be administered to patients who underwent cognitive testing during their Core Study.

Table 9.1.11.6-1 Neuropsychological Protocol for Epilepsy Patients Treated with Cannabidiol - Patient Measures			
Function	Patient Measures	Age Range	Approximate Administration Time for Psychometrician
Intelligence IQ	WPPSI-4 Vocabulary, Matrix Reasoning	2;6 - 5;11 years	30 minutes
	WASI-2 Vocabulary, Matrix Reasoning (Including Wechsler: 'Digit Span' subtest from WISC-4 and WAIS-4; 'Coding' subtest from WISC-4 & WAIS-4; 'Bug Search' from WPPSI-4)	6 - adult	45 minutes
Attention/Executive Trail Making	Trail Making Test D-KEFS	9 - adult	5 minutes
Language Naming Fluency	Expressive One-Word Picture Vocabulary Test-4 th Ed	2 - adult	5 minutes
	NEPSY-2 Word Generation	2 - 5 years	5 minutes
	F-A-S and Animals	6 - adult	5 minutes
Visual-Spatial VMI	Developmental Test of Visual Motor Integration-6	2 - adult	5 minutes
Fine Motor Speed Pegs	Purdue Pegboard	4 - adult	5 minutes

Table 9.1.11.6-2 Neuropsychological Protocol for Epilepsy Patients Treated with Cannabidiol - Parent Measures			
Function	Parent Measures	Age Range	Approximate Administration Time for Parents
Executive	Behavior Rating Inventory of Executive Function (Parent and Teacher)	3 - 21 years	10 minutes
Attention	ADHD Checklist (Parent and Teacher)	All ages	5 minutes
Mood/Anxiety	BASC-2 (Parent and Teacher)	3 - 21 years	20 minutes
Free-form Report	Behavior Report Form (Parent and Teacher)	All ages	5 minutes

9.1.11.7 Cannabis Withdrawal Scale (18 Years and Above) or Pediatric Cannabinoid Withdrawal Scale (4–17 Years)

The CWS is to be administered to patients 18 years of age and above. It is a 19-item scale with each item (withdrawal symptom) measured on a 0–10 NRS (0 = Not at all; 5 = Moderately; 10 = Extremely). The patient or their caregiver is asked to record the extent to which each withdrawal symptom was experienced in the last 24 hours and also to rate the negative impact on normal daily activities (i.e., 2 separate scores are recorded for each item using the same 0–10 NRS). Scores are summed over the 19 items for each measure.

The PCWS is to be administered to patients aged 4 to 17 years of age (inclusive). It was developed from the 19-item validated CWS (adults) that assesses mood, behavioral and physical symptoms associated with cannabis, which was based on the Marijuana Withdrawal Checklist. The modified 10-item PCWS was developed from a low literacy version of the CWS. Symptoms specific to adult cannabis withdrawal have been removed and the wording has been amended to be comprehensible to children of the specified age range.

Ratings are based on a 4-point scale where 0 = none, 1 = a little bit, 2 = quite a bit, and 3 = a lot. This rating scale has been compacted from the original 11-point Likert scale used for the CWS in order to simplify the range of options to consider for potential intellectually disabled children. The PCWS was designed with epileptic children in mind as a tool to assess the safety of cannabinoid medications with respect to the stimulation of cannabinoid withdrawal syndrome when medications are withdrawn. As there may be a wide range of intellectual or developmental difficulties in severely epileptic children, from no intellectual or developmental impairment to extreme, the PCWS has been designed to be administered by a treating clinician, either directly to the child, or to the parent or caregiver of the child, reflecting on the child's symptoms within the chosen timeframe.

The CWS or PCWS, as appropriate, would have been used at the Baseline of the Core Study to establish a baseline score for this current study, GWEP1415.

Assessments will be conducted only if patients are of an appropriate age (4 years of age and older).

9.1.11.8 Menstruation

For female patients, details of menstruation recorded during the Core Study (including whether the patient is menstruating and any changes in normal menstrual cycles) will continue to be assessed.

9.1.11.9 Tanner Staging

The pubic hair growth (both sexes), genital (males only) and breast (females only) development of all adolescent patients (i.e., 10 to less than 18 years of age at the time of signing the informed consent/assent form, or earlier if clinically indicated by onset of menarche or other signs of precocious puberty) will be assessed using Tanner Staging (see [APPENDIX 3](#)). The patients will undergo a discreet physical examination and assigned a value under each category of Pubic Hair Growth (both sexes), Genitals (male patients only), and Breasts (female patients only). Once a patient reaches a score of "V" (i.e., 5), the examination need not be performed again.

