9.2.6 Visit 7 (48 weeks)

Visit 7 will take place 12 weeks after Visit 6 (48 weeks after Visit 1). A visit window of ± 7 days from the scheduled visit date is permitted, but it is preferred that the visit is performed on the scheduled visit day where possible.

The following assessments will be made: vital signs, physical examination (including height and body weight), effects on menstruation cycles (for females), Tanner Staging (for patients aged 10–17 [inclusive], or earlier if clinically indicated by onset of menarche or other signs of precocious puberty), ECG, C-SSRS, Vineland-II, cognitive assessment battery (participating centers only), QOLCE/QOLIE, S/CGIC and S/CGICSD. Clinical laboratory samples (urine [where possible] and blood) will be taken for determination of serum IGF-1 levels (for patients less than 18 years of age), pregnancy (if appropriate, using a serum sample), hematology, biochemistry and urinalysis. The patient's IVRS report and paper diary will be reviewed and the information recorded along with information regarding AEs, IMP, epilepsy-related hospitalizations, concomitant medications and/or changes to medication. The Investigator must assess adherence to the dosing regimen.

The cognitive assessment battery will only be administered at a sub-group of centers that have the expertise to conduct the assessments (ideally before any other study procedures but can be completed on a separate day, if necessary, within 3 days of the visit) and will only be administered to patients who underwent cognitive testing during their Core Study.

A 14-week supply of IMP will be issued to the patient/caregiver.

Following Visit 7, safety telephone calls must be made every 4 weeks (± 7 days) to assess AEs, epilepsy-related hospitalizations, concomitant medications and/or changes to medication. In addition, during titration of doses above 20 mg/kg/day, safety telephone calls must be made every 7 days (± 3 days) until stable dosing is achieved.

At least 1 dispensing appointment will be scheduled to occur between Visits 7 and 8. The dispensing appointment date(s) will be calculated from Visit 7. At each dispensing appointment caregivers will be dispensed with sufficient IMP to be administered until the next scheduled appointment. Patients need not attend the dispensing appointments.

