4. STATISTICAL METHODS

4.1 General Considerations

All tables will be presented by indication (where appropriate), including an overall count, as follows:

Dravet Syndrome (N=XX)	Lennox-Gastaut Syndrome (N=XX)	Overall (N=XX)
------------------------	--------------------------------	----------------

In all tables, listings and figures, the study visits will be referred to and labelled as per [Table 2](#)

Table 2 Study Visits

Actual Visit	Visit Label
Visit 1: Day 1	Day 1
Visit 2: Day 15	Day 15
Visit 3: Day 29	Day 29
Visit 4: Day 85	Day 85
Visit 5: Month 6 or Week 24	Week 24
Visit 6: Month 9 or Week 38	Week 38
Visit 7: Week 48 or End of Treatment (only patients who completed at 1 year)*	Week 48
Visit 8: Week 76	Week 76
End of Treatment (only patients who completed on or after Day 400)*	End of Treatment

End of Treatment (withdrawn patients only)	End of Treatment
End of Taper	End of Taper
Post-Taper Safety Call	Post-Taper Safety Call
Safety Follow-Up	Safety Follow-Up

* For some patients, the end of treatment visit occurs after one year in the OLE, whereas for other patients the end of treatment visit occurs after two or more years in the OLE.

Unless stated otherwise, continuous variables will be summarized showing the number of non-missing values (n), mean, standard deviation, median, minimum and maximum and categorical variables will be summarized showing the number and percentage of patients falling in each category. For continuous summaries of seizure frequency, the lower and upper quartiles will also be presented.

Minimum and maximum values will be presented to the same decimal precision as the raw data. Mean and median will be presented to one more decimal place than the raw data, and standard deviation to 2 more decimal places than the raw data. Percentages will be presented to one decimal place.

For patients who enter the OLE on the same day as the core study end of treatment or end of taper visit, the CRF for this study did not require some data to be entered for a second time. Hence, for visit based endpoints, if a patient does not have data entered in this study at Visit 1, then data from the end of treatment or end of taper visit in the core study will be used, provided that the date of collection is on Day 1 of the OLE.

Unless otherwise stated, all summaries will be presented by indication.

All analyses and summaries will be produced using SAS Version 9.4.

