4.1.2 Handling of Missing Data

4.1.2.1 Seizure Data

If a patient withdraws during the time after which they have taken their first dose in the OLE, then seizure frequencies will be calculated from all the available data prior to the patient withdrawing.

Last observation carried forward (LOCF) methodologies that will be carried out on seizure data are discussed in Section 4.5.9.

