4.5.8.11 Growth and Development

IGF-1 levels will be analyzed as part of the clinical laboratory testing. IGF-1 levels will be summarized on a continuous scale, including change from baseline.

The pubic hair growth (both sexes), genital (males only) and breast (females only) development of all adolescent patients (i.e., 10 to less than 18 years of age at the time of signing the informed consent form, or earlier if clinically indicated by onset of menarche or other signs of precocious puberty) will be assessed using Tanner Staging. The patients will undergo a discreet physical examination and be assigned a value under each category of pubic hair growth (both sexes), genitals (males only), and breasts (females only).

Patients will be examined at Visit 1 (Day 1) and the end of treatment visit. Once a patient reaches a score of V (i.e., 5) the examination need not be performed again.

Tanner Stages will be summarized on a categorical scale.

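### Tanner examination may stop at Stage V, but the SAP neither carries Stage V forward nor defines a denominator, so Table 14.5 can understate pubertal progress

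*Protocol*

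**What the plan says.** Protocol 9.1.11.9 has each adolescent "assigned a value under each category of Pubic Hair Growth (both sexes), Genitals (male patients only), and Breasts (female patients only". For a patient at score V it adds: "i.e., 5), the examination need not be performed again". SAP 4.5.8.11 gives the same permission: "Once a patient reaches a score of V (i.e., 5) the examination need not be performed again".

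The planned analysis is a single sentence in SAP 4.5.8.11: "Tanner Stages will be summarized on a categorical scale". It produces Table 14.5 on the safety analysis set. The general rule in SAP 4.1 is that "categorical variables will be summarized showing the number and percentage of patients falling in each category", and no denominator is given for Tanner stage.

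The missing-data rules in SAP 4.1.2 cover seizures, adverse events and concomitant medication. Carry-forward is mentioned for one of these only: "Last observation carried forward (LOCF) methodologies that will be carried out on seizure data are discussed in Section 4.5.9". Protocol section 9 requires examinations that were not carried out to be recorded on the CRF as not done.

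The schedules differ. SAP 4.5.8.11 says: "Patients will be examined at Visit 1 (Day 1) and the end of treatment visit". Protocol 9.2.6 (Week 48) lists "effects on menstruation cycles (for females), Tanner Staging (for patients aged 10–17 [inclusive], or earlier if clinically indicated by onset of menarche", and Protocol 9.2.8 and 9.2.10 add Weeks 104 and 156.

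**The concern.** The permission excuses patients from examination only because they have reached the top stage, so the resulting missing values depend on the outcome itself. A skipped patient is recorded as not done, although the stage is known. A table built from recorded examinations then compares a Visit 1 row that contains the Stage V patients with later rows that have lost some or all of them.

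Growth and development in patients under 18, including Tanner staging, is a secondary endpoint defined as change from the Core Study baseline, and SAP 4.7 does not drop it. With a single treatment group, Table 14.5 can be read only against baseline or expected development. Understated maturation in that table would look like slowed puberty, which is the signal that the assessment exists to detect.

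**Working it through.** The documents give no Tanner figures, so there is nothing to reproduce. All percentages below are illustrative.

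**Direction.** Let B be the share at V at Visit 1, T the true share at V at the later row, N = T − B the share newly at V, and s the fraction of the B patients who are skipped. Assume no dropout and that everyone else is examined.

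- Shown share, patients examined as denominator: (T − sB) / (1 − sB).
- Shown minus true: −sB(1 − T) / (1 − sB). This is negative whenever anyone is skipped and T is below 100%.
- Shown share, all patients as denominator: T − sB, also below T.

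Both readings of the missing denominator therefore understate Stage V.

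**Size on the SAP schedule (Visit 1 and End of Treatment).** B and T are assumed.

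| B | True T | Shown, all skipped (s = 1) | Shown, half skipped (s = 0.5) |
|---|---|---|---|
| 25% | 50% | 25/75 = 33.3% | 37.5/87.5 = 42.9% |
| 15% | 40% | 25/85 = 29.4% | 32.5/92.5 = 35.1% |
| 35% | 62% | 27/65 = 41.5% | 44.5/82.5 = 53.9% |

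With all patients as denominator and s = 1, the first line shows 25/100 = 25%: no progress, against a true doubling.

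**When the share appears to fall.** The shown share is below B only if N < sB(1 − B). In the three lines N is 25, 25 and 27 points. The limits at s = 1 are 0.25 × 0.75 = 18.75, 0.15 × 0.85 = 12.75 and 0.35 × 0.65 = 22.75 points. None of them falls, even with complete skipping.

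**Illustration from the Appendix 3 ages.** Assume ages uniform from 10 to under 18 at Day 1, Stage V reached at exactly 15 years (girls) or 14 years (boys), no dropout, and follow-up regardless of later age. Then B = 3/8 = 37.5% for girls and 4/8 = 50.0% for boys. Week 48 (336/365.25 = 0.92 years) adds 0.92/8 = 11.5 points and Week 104 (728/365.25 = 1.99 years) adds 24.9 points.

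| End of Treatment at | Sex | Visit 1 | True | Shown, s = 1 |
|---|---|---|---|---|
| Week 104 | Girls | 37.5% | 62.4% | 24.9/62.5 = 39.9% |
| Week 104 | Boys | 50.0% | 74.9% | 24.9/50.0 = 49.8% |
| Week 48 | Girls | 37.5% | 49.0% | 11.5/62.5 = 18.4% |
| Week 48 | Boys | 50.0% | 61.5% | 11.5/50.0 = 23.0% |

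At Week 104 progress almost disappears; at Week 48 the share appears to fall. With half skipping, girls show 37.2% at Week 48, essentially level with Visit 1, and 53.7% at Week 104.

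If the Protocol's intermediate rows were tabulated with complete skipping, girls would show 18.4%, 26.3%, 33.1% and 49.6% at Weeks 48, 104, 156 and 208 (true 49.0%, 62.4%, 74.9% and 87.3%). The deepest fall is in the first later row. With half skipping the Week 48 and Week 104 values are 37.2% and 50.2%.

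**The case against.** The permission is not an instruction. Sites may go on examining Stage V patients, and SAP 4.5.8.11 does not rule out a derivation step when Table 14.5 is programmed. That stands, and it is why the size cannot be stated. It does not supply the missing rule: SAP 4.1.4.2 defines a last visit for clinic-visit endpoints, but the Tanner subsection does not use it.

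The consequence is limited. Tanner stage is one component of one descriptive secondary endpoint, nothing is tested, and Listing 14.6 shows each patient's stages, so the table can be corrected later. This lowers the stakes but leaves the planned table uncorrected.

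A reader might infer three stronger claims that the documents do not support:

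- **That the table will show puberty going backwards.** On the SAP's own two-visit schedule the 25%, 15% and 35% examples all rise. SAP Table 2 has no Week 104 label, so a Week 104 row is not an evident SAP output.
- **That a girl leaves follow-up when only one feature reaches V.** The female form in Appendix 3 tells the rater to take the lower stage as the overall score when features differ. The male form has no such rule, and Protocol 9.1.11.9 and SAP 4.5.8.11 speak of a value per category. That inconsistency is what remains.
- **That a patient who reached V in the Core Study never appears.** This depends on Core Study rules that are not in these documents. Protocol 9.2.1 requires re-assessment at Visit 1 after any dosing gap and otherwise treats Core End of Treatment staging as Visit 1 data.

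**Conclusion.** The point holds as an understatement of maturation. Both documents let only Stage V patients leave the examination schedule, and nothing in the SAP puts them back into the table. To the extent that the permission is used, later rows understate the Stage V share, whichever denominator is chosen.

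The amount depends on site practice. With an assumed 25% at V at Visit 1 and a true 50% at End of Treatment, the shown share is 33% with complete skipping and 43% with half skipping. Both figures assume no dropout and examination of everyone below V. An apparent reversal is not the general expectation: it needs early rows or short follow-up, and is sizeable only when nearly all Stage V patients are skipped.

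**What to change.** In SAP 4.5.8.11 and the specification of Table 14.5, add a derivation rule. Once Stage V is recorded, in the Core Study or the extension, carry it forward for that category (or for the overall score, if that is what is collected) to every later Tanner visit the patient attends. Base percentages on patients still in the study with a recorded or carried-forward stage.

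Two reconciliations belong with it:

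- Align the per-category wording of Protocol 9.1.11.9 and SAP 4.5.8.11 with the lesser-stage rule in Appendix 3, now given for females only, so that the stop permission is read the same way for both sexes.
- Reconcile the SAP's Tanner schedule with the Protocol's additional visits, because the schedule decides which rows exist.

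The carry-forward costs one SAP sentence and a small programming change, and needs no new data. The scoring clarification is a short text edit; depending on how it is settled, it could mean a few extra stagings at visits already held.
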